Feasibility studies are used to determine whether an intervention is appropriate for further evaluation, to determine sample sizes for controlled trials and to assess whether the ideas and findings can be shaped to be relevant and sustainable. In this study, the feasibility of training volunteers to deliver a virtual multi-modal intervention to improve older adult's functional outcome post-discharge will be assessed. The acceptability of the intervention will also be examined through qualitative interviews to explore the views and experiences of volunteers, trainers, carers and older adults involved in this study. The impact of the intervention on physical activity levels and functional outcomes will be measured. However, as this is a feasibility study, it is not powered to show any statistical difference in the outcome measure.

Intervention

The intervention duration will be 3 months. Participants will receive three group sessions per week for 1 month (weeks 1-4), twice per week for the second month (weeks 5-8), and once weekly for the last month (weeks 9-12), with a maximum of 24 sessions. The tapered nature of the intervention was chosen to provide suitable support for older adults post-discharge with the aim to gradually encourage increased self-management to foster independence post-intervention. Components of the intervention, including exercise, nutrition support and behaviour change support, will be delivered from an online platform (Zoom). Each group session will last 40-60 minutes, including 20-30 minutes of exercise

followed by 20-30 minutes of nutrition support. The components of the intervention and the training package have been adapted from the SafeFit trial [35] and will be delivered in line with behaviour change principles and emotional support to maximise participant uptake, adherence and lifestyle self-management.

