Nutrition support: Volunteers will work with participants to review their diet and eating habits using the Nutrition Wheel to ensure their nutrition is appropriate and they are not at risk of undernutrition [31]. The Nutrition Wheel is an interactive tool developed from the Patients Association Nutrition Checklist (PANC) and used to engage individuals in conversation about unintentional weight loss and malnutrition. The Nutrition Wheel was developed by [name] in collaboration with the Wessex AHSN and key stakeholders and charities and identifies whether an older adult may be at risk of undernutrition, providing guidance accordingly. Specifically, the Nutrition Wheel consists of 4 main questions from PANC, including 1) Are you or your family concerned that you may be underweight, or need nutritional advise? 2) Have you lost a lot of weight unintentionally in the past 3-6 months? 3) Have you noticed that your clothes or rings have become loose recently? 4) Have you recently lost your appetite and/or your interest in eating? Based on the participant's answers, they will be directed to further questions and guided to appropriate nutritional advise. Individuals identified as undernourished will be signposted to appropriate information sheets, national helplines, or if necessary, signposted to their GP/practice nurse for further advise and screening.

Behaviour change support: Volunteers will receive training in healthy conversation skills (HCS) guided by principles of Making Every Contact Count (MECC) [52, 53]. The MECC approach supports positive behaviour change through encouraging client-centred brief conversations surrounding health and well-being and will help support the delivery of the exercise and nutrition components in the current intervention. Training will enable volunteers to have the confidence and competence to deliver healthy lifestyle messages, to help encourage participants to change their behaviour through solution-focused and empowering approaches [54]. The MECC approach is underpinned by behaviour change principles from the COM-B model, highlighting both automatic and reflective processes involved in decision making and action. Through using HCS in the current intervention volunteers can help to improve participants capability and motivation to be physically active and to eat well, empowering

participants to take control of their health behaviours by building self-efficacy and a sense of control [55].

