Volunteers will be given a training manual to help support their learning and to be used as a resource during delivery of the intervention. Volunteers will also be asked to keep an attendance record during the intervention using session completion logs and will be trained to report any adverse events.

Safety during sessions

Volunteers will be encouraged to complete a pre-session screening checklist to ensure participants are safe to exercise (e.g., safe set-up of a home exercise space; feeling well; no new or worsening symptoms). Volunteers will be taught to encourage participants to exercise at their own pace, to rest when they need to, and to move within a pain-free range of motion, ensuring that participants are working at a tailored intensity. Where possible participants will be encouraged to undertake the sessions with friends or family members present and they will be asked to keep cameras on during the

sessions. If a participant feels unwell a Zoom breakout room will enable the participant's well-being to be reviewed in private by a second volunteer.

If an emergency occurs, such as an acute medical event during the session, the volunteer will encourage participants to call their GP, or 111. If concerned about collapse, the volunteer will call 999. Volunteers will have a list of participant's addresses and GPs to hand - in case of collapse. An 'escalation plan' giving clear steps to follow, depending on the emergency situation, will be given to volunteers.

Data Collection

Participant characteristics including age, gender, domicile status, weight, body mass index, malnutrition status (MUST), baseline nutritional status (e.g., use of nutritional supplements and dietician support), co-morbidities (Charlson Co-morbidity Index) [57], cognition (Mini-mental state examination; MMSE) [58] and number of medications will be recorded. Volunteer characteristics recorded will include age, occupation, qualifications, volunteering experience, and employment status.

The primary outcome measures are feasibility and acceptability of the intervention.

Feasibility

The feasibility of implementing a volunteer-led online multi-modal intervention will be assessed by determining the number of volunteers recruited, trained and retained at the end of the study, the number of intervention sessions delivered and fidelity of volunteer delivery. Moreover, participant recruitment, retention and adherence to the intervention will be measured, as well as any adverse events

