Acceptability of the intervention

Interviews will be conducted among older adults (N= 6), volunteers (N= 6), and those involved in recruiting participants and training volunteers (N= 3), to determine the acceptability of the intervention and to explore barriers and enablers to the implementation of the intervention. Interviews will be semi-structured to help guide conversation whilst allowing participants the flexibility to elaborate and reflect on any meaningful experiences.

Older adults will be selected by purposive sampling to share their thoughts and views regarding the implementation of the volunteer-led sessions. To ensure a wide range of views are included in the interviews, participants will be selected to ensure equal distribution of male and female patients, ethnicities, and a representative age range. Interviews will also be conducted for volunteers leading the intervention. Discussions among volunteers are likely to generate a wider perspective of the implementation process and may provide insight into the group narrative on their experiences in delivering the intervention and their interaction with the research participants. Interviews will be conducted via telephone and will be audio-recorded for data collection purposes.

The interviews will be semi-structured and consist of several key open-ended questions that will help define the areas explored but allow the interviewer or interviewee to expand and diverge with the aim

of pursuing or developing an idea with more depth. The interview schedules will be underpinned by Normalisation Process Theory (NPT) (see below). The interviews will seek to explore the views of older adults, volunteers and trainers on the multi-component sessions, the barriers and facilitators to the intervention and suggestions for future implementation studies.

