Data collected from the interviews will be transcribed verbatim and analysed using thematic analysis (TA). The audio-recordings will be transcribed by an administrative colleague within the research department who is experienced in transcribing qualitative data. TA is a method for identifying, analysing and reporting patterns or themes within data and is widely used in qualitative research [75]. There are six phases in the process of conducting TA: Phase 1 – familiarising with the data, Phase 2 – generating initial codes, Phase 3 – searching for themes, Phase 4 – reviewing themes, Phase 5 – defining and naming themes, and Phase 6 – producing the report. Analysis of qualitative data will be conducted using either Microsoft Word, or with the help of NVIVO, depending on the amount of data collected. Transcribed text will be read and coded separately and then together by two researchers. The codes will be analysed to generate concepts and ideas to determine the acceptability of the intervention, and to identify facilitators and barriers to the implementation process. The codes act as tags or labels to help catalogue key concepts embedded within the raw data. From the codes, themes will be developed to reflect the views and experiences of the community-dwelling older adults and volunteers regarding the community-based PA intervention.

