6 STUDY SETTING

This is a single-centre feasibility study taking place at University Hospital Southampton NHS Foundation Trust. Patients on the discharge pathway will be identified and recruited from acute medical wards at UHS and volunteers will be recruited from UHS voluntary services. Volunteers will complete study training at UHS and will deliver the online intervention from UHS. Recruited older adults with frailty will participate in an online intervention from their own home upon discharge from hospital. Interviews will take place on the phone, or an online platform while participants are at home.

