- 8. What are your views on the use of trained volunteers to deliver group exercise and nutrition support to older people in the community?
 - a. Can you describe your experience with these exercise and nutrition sessions? Any advantages or disadvantages?
 - b. What was good about these groups? And what things do you think need improvement?
 - c. What were the benefits?
 - d. Were there negative experiences?
- 9. In your view, how effective were the trained volunteers at delivering the exercises and encouraging participants to be more active?
- 10. In your view, how effective were the trained volunteers at delivering the nutrition wheel and encouraging participants to eat healthily?
- 11. Do you have any suggestions or comments about the intervention?
 - a. Explore things that went well
 - b. Explore things that could be improved
- 12. What were your experiences with using the device and receiving the support online?
 - c. Explore any barriers to accessing, or using the online intervention e.g., tech knowledge, general perceptions of using technology, any misconceptions regarding online platforms, visibility and sound during sessions
 - d. Explore the things that helped / facilitated use of online tech
- 13. In your opinion, how could these volunteer-led sessions be continued and extended to other clubs?
 - c. Explore participants views on barriers and facilitators to the implementation of the intervention in other settings

Frail2Fit study

Semi-structured interview schedule for family members

- 1. Since being discharged from hospital how have things been going for your family member at home?
 - e. Could you explain what a typical day is like for them? (Build rapport and understand what life is like for them)
 - f. Explore functional capacity
 - g. Explore meaningful activities and general day to day motivation
 - h. Explore any concerns or barriers to recovery post-discharge
- 2. Tell me your views about being physically active in general.
 - e. Explore general perception on physical activity
 - f. What are the potential benefits?
 - g. Any potential harm?
- 3. In your view, what are the things/factors that could discourage older people to be more active?
 - a. Explore environmental factors, motivation, cost, accessibility, fear of injury/falls
- 4. What are the things/factors that could encourage older people to be more active?
 - c. Explore environment, social support, interest, accessibility

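### The interview guides for acceptability ask about extending sessions to 'other clubs' and have no dedicated question on behaviour change support, and the theme statement is worded for a physical activity intervention

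*Combined protocol and SAP*

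**What the plan says.** Section 5 (Data Collection) states: "The primary outcome measures are feasibility and acceptability of the intervention". Under the acceptability heading it assigns that outcome to interviews with 6 older adults, 6 volunteers and 3 people involved in recruitment or training, and gives their scope: "The interviews will seek to explore the views of older adults, volunteers and trainers on the multi-component sessions, the barriers and facilitators". The study design text in section 5 adds carers to the groups whose views are sought.

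The aim in section 4 and the intervention text in section 5 name three components: exercise, nutrition support and behaviour change support. Section 6 gives the setting: "Recruited older adults with frailty will participate in an online intervention from their own home upon discharge from hospital".

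Three interview guides are appended, for volunteers, patients and family members. Volunteer question 14, patient question 13 and family question 13 share one stem: "In your opinion, how could these volunteer-led sessions be continued and extended to other clubs". Each is followed by a probe on barriers and facilitators in other settings.

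The section 5 text on qualitative analysis ends by saying that "themes will be developed to reflect the views and experiences of the community-dwelling older adults and volunteers regarding the community-based PA intervention".

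**The concern.** Objective 4 asks for acceptability, and for barriers and facilitators that will support wider implementation. Sections 4.2 and 9.1 look ahead to roll-out across a region and later nationally. The instruments and the analysis statement should therefore describe the intervention and setting being tested. In three places they do not:

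- **Roll-out question.** The stem names a setting that the study does not use.
- **Behaviour change support.** One of the three components has no question of its own.
- **Theme statement.** It names one type of intervention and two of the interviewed groups.

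At stake is how directly the interviews can answer objective 4. Interviewees may answer the roll-out question about clubs they have no experience of. Views on goal setting and on the style of conversation may surface only if someone happens to raise them. An analyst who followed the closing sentence literally would also have grounds to leave out material that the rest of the plan wants.

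**Working it through.** No arithmetic on effect sizes or sample size applies. The protocol says of itself that "it is not powered to show any statistical difference in the outcome measure", and this point changes no statistical figure. The check is an item-by-item reading of the three guides against the intervention, the setting and the analysis text.

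**Step 1: coverage by guide** (V = volunteers, 15 questions; P = patients, 13; F = family, 13)

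| Topic | V | P | F | Guides |
|---|---|---|---|---|
| Roll-out stem naming 'other clubs' | Q14 | Q13 | Q13 | 3 of 3 |
| Probe on other settings under that stem | Q14 | Q13 | Q13 | 3 of 3 |
| Volunteers delivering or encouraging exercise or activity | Q9 | Q9 | Q9 | 3 of 3 |
| Nutrition Wheel and encouraging healthy eating | Q10 | Q10 | Q10 | 3 of 3 |
| Item naming behaviour change support, healthy conversations or goal setting | none | none | none | 0 of 3 |
| Open question on the intervention | Q12 | Q11 | Q11 | 3 of 3 |
| Online delivery | Q13 | Q12 | Q12 | 3 of 3 |
| Life at home since discharge | none | Q1 | Q1 | 2 of 3 |
| Volunteer training | Q11 | none | none | 1 of 3 |

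**Step 2: the roll-out stem.** Section 6 places the intervention online in the participant's home, and no club appears in the design. In the patient and family guides this is the only question on wider implementation. The probe widens the topic, but only after the stem has pointed the interviewee to clubs.

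**Step 3: behaviour change support.** Section 5 says the approach "will help support the delivery of the exercise and nutrition components in the current intervention". It has no separate slot in the session, so some of it will be heard in answers about encouragement. Its training, however, is a 3-hour session, against 2 hours for nutrition, and aims at four skills: open questions, listening in place of advising, reflecting, and structured goal setting. A question on whether volunteers encouraged people to be active does not reach listening or goal setting. Question 8 in each guide also frames the sessions as exercise and nutrition support only.

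**Step 4: the analysis statement.** The same paragraph of section 5 holds two scopes. An earlier sentence has the codes judge acceptability of the intervention and identify barriers and facilitators, with no restriction by component. The closing sentence limits the themes to physical activity, to a community-based setting, and to older adults and volunteers. The acceptability text plans multi-component scope and interviews with trainers, and the study design text adds carers. The closing sentence agrees with none of these.

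**Step 5: room to recover.** Section 5 plans 6 patient and 6 volunteer interviews, and the Schedule of Procedures gives one interview each, of 25 to 45 minutes. The synopsis gives larger numbers (15 patients and their family members or carers, and 10 volunteers). On either count a topic missed by the guide depends on being raised unprompted.

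**The case against.** A reader might infer that part of the intervention and its setting goes unevaluated. The documents do not support that. The patient and family guides open with life at home since discharge, all three guides ask about online delivery, and the roll-out stem carries a probe on other settings.

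A reader might also infer that behaviour change support will yield no data. That is too strong as well. It is the manner in which the other two components are delivered, so the encouragement questions touch it. Volunteers are asked about training content, which includes healthy conversation skills. Every guide has an open question, and section 5 lets the interviewer diverge. Fidelity checks assess behaviour change competence, and a self-efficacy scale is collected. What stands against this is narrower. Fidelity checks measure whether volunteers deliver the approach, and the scale measures participants' confidence in managing their disease. Neither says whether the approach was acceptable.

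The closing analysis sentence might be read to mean that only physical activity will be reported. The coding aim in the same paragraph covers the intervention as a whole, so the text is inconsistent rather than restricted.

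Finally, the general questions on activity and diet in the patient guide might be thought to crowd out the intervention. Question counts do not measure interview time, and those questions bear on barriers and facilitators. Their order is a matter of preference.

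**Conclusion.** The point holds as a defect of wording and coverage in the instruments for a primary outcome. The roll-out stem names an unused setting in 3 of 3 guides. One of three components has a dedicated question in 0 of 3 guides, while the other two have one in every guide. One analysis sentence conflicts with the scope stated elsewhere in section 5. The setting, online delivery and, indirectly, behaviour change support are still covered, so this weakens the answer to objective 4 without removing it.

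It should be changed because acceptability rests on few interviews that cannot readily be repeated, and the correction is small. The conclusion assumes that the appended guides are the ones in use and that interviewers follow their stems. An interviewer who routinely adds questions on goal setting would narrow the gap, but the plan does not require it.

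**What to change.** 1. In volunteer Q14, patient Q13 and family Q13, replace the reference to clubs with wording that matches the planned roll-out, for example: *offered to people leaving hospital in other places*. Keep the existing probe.
2. Add one stem on behaviour change support to each guide. For patients: *How did you find the conversations with the volunteers about changes you wanted to make, and any goals you set?* Adapt it for family members (what they noticed) and for volunteers (how they found using the approach).
3. Redraft the closing sentence of the qualitative analysis text, for example: *Themes will cover every group interviewed, including trainers and carers, and the exercise, nutrition and behaviour change components of the online intervention after discharge.*

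No extra interviews are needed. The added stem should take a minute or two (an estimate). Against the planned 25 to 45 minutes that is between 1/45 = 2% and 2/25 = 8% of the interview. The changes need an amendment, and section 8.2 leaves its classification to the sponsor. If some interviews are already complete, the analysis sentence can still be corrected, and the report should say that those interviewees were not asked directly about behaviour change support.

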1 BACKGROUND

Older people with frailty are at high risk of poor outcomes including increased post-hospitalisation, healthcare use and mortality [1]. Frailty refers to a state of vulnerability to poor resolution of homeostasis after a stressor event and results from a cumulative decline in biological reserves across multiple organ systems [2]. Approximately 11% of community dwelling older adults have frailty [3], compared to around 14% prevalence in English hospitals [4]. As frailty progresses older adult's functional status declines, resulting in disability, increased risk of falls, and long-term care [5]. Moreover, deconditioning during hospital admission is a major concern and impacts significantly on older adult's ability to be independent. Hospitalised older adults are at risk of immobilisation resulting in reductions in muscle mass by 0.5% and muscle strength by 0.3-4.2% per day [6, 7]. Considering these detrimental clinical consequences, identifying vulnerable patients with frailty, and intervening to prevent functional decline is a high-priority patient-centred outcome.

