8 ETHICAL AND REGULATORY CONSIDERATIONS

8.1 Assessment and management of risk

There are minimal risks involved in this study. This study does not involve any invasive procedure. It is perceived that the benefits of the intervention outweigh potential risks. Studies have shown that exercise training and nutrition support are beneficial in improving physical function of older people. One of the benefits of taking part in the study is that volunteers and patients will be taught evidence-based exercises and nutrition advice which will be conducted in group online sessions. Moreover, exercising in an online group can also be a positive experience as the social aspect of group exercises has been shown to be a source of motivation.

Although the risks involved in the study are minimal, common injuries that may occur during exercises include muscle strain and back pain. Nevertheless, these risks will be reduced through various approaches explained below. Hospital volunteers are covered by NHS indemnity insurance in the case of any adverse events.

- Volunteers will complete evidence-based training modules to ensure they are competent to deliver the intervention to frail older adults. All volunteers recruited by voluntary services at the hospital have completed generic safety checks (e.g., criminal record checks) and basic training (e.g., health and safety).
- Volunteers will be taught to encourage participants to exercise at their own pace, to rest when they need to, and to move within a pain-free range of motion, ensuring that participants are working at a tailored intensity.
- Throughout the study period, fidelity checks will be conducted by the trainers once every 2 weeks to ensure that the volunteers are delivering high quality group sessions. The volunteers will be observed and assessed against a competency and implementation checklist, including competency checks for the exercise, nutrition, and behaviour change components.
- Volunteers will complete a pre-session screening checklist to ensure participants are safe to exercise (e.g., safe set-up of a home exercise space; feeling well; no new or worsening symptoms).
- Where possible participants will be encouraged to undertake the sessions with friends or family members present and they will be asked to keep cameras on during the sessions.
- If a participant feels unwell a Zoom breakout room will enable the participant's well-being to be reviewed in private by a second volunteer.

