11. APPENDICIES

11.1 Appendix 1- Required documentation

CV of Chief Investigator

Participant Information Sheet

Participant Consent Form

Consultant Letter

Referee's Report

Letter from Funder

Data Collection Booklet

Interview Schedule

Screening and Escalation Plan

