 - e. Explore any barriers to accessing, or using the online intervention e.g., tech knowledge, general perceptions of using technology, any misconceptions regarding online platforms, visibility and sound during sessions
 - f. Explore the things that helped / facilitated use of online tech
- 13. In your opinion, how could these volunteer-led sessions be continued and extended to other clubs?
 - a. Explore participants views on barriers and facilitators to the implementation of the intervention in other settings

Screening and Escalation Plan

Screening at the start of each support session (5-10 minutes)

- Exercise: It is essential to use Table 1 (Exercise Screening at each Session)to identify any changes in participant-specific considerations (or comorbidities)and if necessary, to take the appropriate action defined in Figure 1 (Escalation Process). Please also report any actions taken or concerns to the Frail2Fit team on (insert number here), or (insert email here).
- **Nutrition:** Any marked change in appetite, eating habits (including change inability to eat or drink) and perceived unintended weight loss: Do not exercise and notify trial team on (insert number and email here).
- **Medications:** If participant has started any new medications, report this to the Frail2Fit team. Ensure patient has taken prescribed medications as normal. If they haven't contact the Frail2Fit team on (insert number and email here).

If a concern arises please refer to the **SAFETY ESCALATION PROCESS** outlined in Figure 1.

Table 1. Exercise Screening at each Session

Has the participant been experiencing any of the following?

Delayed onset muscle soreness

If yes, observe and modify exercises accordingly

Has the participant experienced any of the following?

Contacted GP

Visited A&E

Been admitted to hospital?

If yes, please contact Frail2Fit trial team before delivering the exercise support session.

Has the participant experienced any of the following?

Fever or infection

Nausea, vomiting or diarrhea

Recent dizziness or fainting

Any new or worsening of symptoms (e.g., pain)

If yes, no exercise - alert trial team

Emergency Scenario

Chest, arm or jaw pain Dial 999

Anything that the instructor feel's is an emergency

When appropriate please alert the Frail2Fit team

Safety Escalation

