Based on your screening results you may need to escalate to the trial team for further advice before proceeding with your session – if this is the case please record this in your session completion log.

There may also be circumstances where you need to escalate during or after your session as outlined in Figure 1.

Patient safety is our highest priority, so if you have any concerns or doubts, please just call us.

KEY REMINDER: Please remember to alert the trial team to **any changes** in the participants' status such as:

- New medical diagnosis or co-morbidity
- Start of new medication and removal of a medication
- Admission to hospital or visit to A&E or GP
- New investigations that have been arranged
- New onset of symptoms or worsening of previous symptoms
- Change in known co-morbidities

Figure 1. Safety Escalation Process

Low Risk

- Defined as a scenario where telephone advice is required
- Ring Frail2Fit team on (insert number here)

Intermediate Risk

- Defined as a scenario where the volunteer is unsure whether proceeding with the session is safe or requires further advice opost session. These scenarios may or may not require further action.
- Ring Frail2Fit team on (insert number here)

Emergency Scenario

- This is defined as anything the volunteer feels is an emergency
- Ring 999 or refer participant to 999 / 111 if able
- When appropriate please alert the Frail2Fit team on (insert number here)

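### The session screening form has no home set-up item, although sections 5 and 8.1 say the checklist covers it, and it has no direct falls prompt

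*Combined protocol and SAP*

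**What the plan says.** Section 5 (Safety during sessions) introduces the checklist this way: "Volunteers will be encouraged to complete a pre-session screening checklist to ensure participants are safe to exercise (e.g., safe set-up of a home exercise space". Its examples in full are "e.g., safe set-up of a home exercise space; feeling well; no new or worsening symptoms". Section 8.1 lists the same checklist among the measures that reduce exercise risk, but words it as "Volunteers will complete a pre-session screening checklist to ensure participants are safe to exercise (e.g., safe set-up of a home exercise space".

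The working document is the Screening and Escalation Plan at the end of the appendices. It instructs volunteers: "It is essential to use Table 1 (Exercise Screening at each Session)to identify any changes in participant-specific considerations". Around Table 1 it adds nutrition and medication prompts, a Key Reminder list of changes to report to the trial team (for example "Admission to hospital or visit to A&E or GP"), and a three-level escalation scheme in Figure 1.

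On falls, section 1 describes progressing frailty as "resulting in disability, increased risk of falls, and long-term care". Section 5 (Feasibility) counts adverse events among the feasibility measures, and feasibility is part of the primary outcome.

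**The concern.** Section 8.1 offers the checklist as a reason to regard the exercise risk as controlled. If the form does not contain the first thing the checklist is said to contain, the control described to the ethics committee and the control on paper differ. The intervention is delivered at home by volunteers, so whatever the form does not ask depends on someone noticing.

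The second issue concerns measurement. With 23 patients, a few events can change how the safety results read. If falls between sessions are recorded only when they also produce a symptom or a care contact, the adverse-event count depends partly on how the form is built.

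**Working it through.** No figure in the plan is in dispute, so the check compares the promised content with the form and then runs cases through the form.

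**1. Promised content against the form**

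| Example in sections 5 and 8.1 | Counterpart in the Screening and Escalation Plan |
|---|---|
| Home space arranged safely | None |
| Participant feels well | Table 1: fever or infection; nausea, vomiting or diarrhoea; dizziness or fainting |
| No new or worse symptoms | Table 1: new or worsening symptoms |

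The remaining Table 1 entries are "Delayed onset muscle soreness", care contact (GP, A&E, admission) and the emergency row. The nutrition prompt concerns appetite, eating and weight. The medication prompt concerns new or missed medicines. The Key Reminder list covers diagnoses, medicines, care contacts, investigations, symptoms and co-morbidities. Figure 1 grades the response. None of these mentions the exercise space or a fall.

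**2. Is there another form?** Appendix 1 names one screening document, the "Screening and Escalation Plan". The documents never state outright that Table 1 is the checklist of sections 5 and 8.1, but no other candidate is supplied.

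**3. Cases run through the form**

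| Case | Row triggered | Stated response |
|---|---|---|
| Unsafe space, participant well | None | None, unless the volunteer notices and rings the team |
| Fall with no symptom, no dizziness or fainting, no care contact | None | None, unless the participant mentions it |
| Fall with pain or another new symptom | New or worsening symptoms | No exercise; team alerted |
| Fall with dizziness or fainting | Dizziness or fainting | No exercise; team alerted |
| Fall leading to GP, A&E or admission | Care contact | Team contacted before the session |

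The gap is complete for set-up. For falls it is confined to the second row of the table.

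**4. Where the set-up gap bites.** On Zoom, participants are asked to keep cameras on, so a volunteer may see the space. Sections 5 and 8.1 also let participants choose telephone consultations at a similar frequency, in which volunteers encourage the booklet exercises. A spoken question is then the only check the volunteer can make.

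**5. Strength of the requirement.** Section 5 has volunteers encouraged to complete the checklist, section 8.1 says they will complete it, and the plan calls use of Table 1 essential. These are three different obligations.

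**6. Size.** Sessions per participant: 3 × 4 + 2 × 4 + 1 × 4 = 24, which matches the stated maximum. With 23 patients (section 7.2.1), 23 × 24 = 552 participant-session screens at most would carry no set-up item. This assumes full recruitment and attendance. It counts screens, not unsafe spaces.

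**The case against.** The case for leaving the form alone has several parts.

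- **Table 1 may not be the whole checklist.** Its stated purpose is to identify changes in the participant. Appendix 1 also omits items the protocol says will be used, such as the session completion logs and the training manual, so its silence does not prove that no other checklist exists. This stands as a caveat. The mismatch between the described content and the supplied form remains.
- **Set-up is handled elsewhere.** Volunteers are taught safe set-up, trainers observe sessions, family or friends are encouraged to be present, cameras stay on and exercises are seated. These measures are real, but none is a check recorded at each session, and cameras do not help on the telephone.
- **The reporting route is open-ended.** The Key Reminder list gives examples only, and a volunteer in doubt is told to ring the team. That works only if the volunteer sees or hears of the problem.
- **No passage promises a falls question.** This stands fully, and it is why the falls point is a content gap only.

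A reader might go further in four ways that the documents do not support:

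- That anyone with a recent fall would be passed to exercise. Three of the four fall cases above meet a row.
- That patients enter on a frailty score and a few steps alone. Section 7.1.2 excludes those whose clinician advises that they cannot safely complete the exercises, and section 7.1.1 has further criteria.
- That unprompted falls are necessarily lost from the adverse events. Section 5 separately says volunteers are trained to report any adverse event, and the log template is not in the documents, so its fields are unknown.
- That a number of affected people can be stated. The documents give no fall rate, so any such number would rest on assumption alone.

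**Conclusion.** The set-up point holds as an internal inconsistency. Two sections name a safe home space as checklist content, one of them as a risk control, and the supplied form has no such item. It rests on reading Table 1 as that checklist and on the table having been extracted completely, which it appears to have been. The three statements on completion also need to be reconciled.

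The falls point holds in a smaller form. A fall without symptoms, dizziness or fainting, or care contact triggers no row and may be missed in the adverse events. It concerns completeness of recording and contradicts nothing in the protocol.

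The ceiling for the set-up gap is 552 screens; the harm is not quantifiable from the documents. The correction is worth making because it is cheap and because section 4.2 foresees wider use of the programme, in which an uncorrected form could be reused.

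**What to change.** 1. Reconcile section 5 (Safety during sessions), section 8.1 and the Screening and Escalation Plan by adding the home set-up item to Table 1, worded so that it can be asked by telephone. State that Table 1 is the checklist the two sections refer to.
2. Use one consistent statement of the completion requirement in all three places.
3. Record any fall since the last session in the session completion log, if it is not already there, as an item for ascertaining adverse events. It is a recording prompt, not an exercise criterion.
4. Leave any action that follows from either item to the investigators.

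The cost is a few seconds per participant per session and a small form revision. The adverse-event count may rise slightly because more events are asked about, and the report should say so.
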